“Nitrous Oxide for Analgesia in Sickle Cell Vaso-occlusive Crisis”

ClinicalTrials.gov ID: NCT01891812

Date of IRB approval: March 28, 2018

Principal Investigator: [name], MD, MPH

Study Purpose and Rationale:

Sickle cell disease (SCD) is an autosomal recessive disorder that produces abnormal hemoglobin and deformed red blood cells. Vaso-occlusive crisis (VOC) is a complication of SCD in which the abnormal red blood cells occlude small blood vessels, causing episodes of severe, unremitting pain. VOC is the most common cause of acute morbidity in SCD, and the number-one reason for hospitalization.(1) The current treatment of VOC consists primarily of opioids and non-steroidal anti-inflammatory medications (NSAID).(2) However, this current approach is inadequate in decreasing the rate of hospitalization for VOC, lengths of stay, and subsequent morbidity. In addition, the repeated and chronic administration of opioids can lead to both short and long term adverse effects, including constipation, hypotension, respiratory depression, seizures, opioid induced hyperalgesia, opioid tolerance, and chronic pain irrespective of VOC episodes.(2-4) Nitrous oxide (N2O) is commonly used for VOC in France despite the absence of randomized trials to determine its efficacy or safety. N2O is a gas that produces analgesia, anxiolysis, and amnesia by NMDA receptor antagonism and release of endogenous opioid peptides (EOP).(5-7) A recent survey of 85 French pediatric emergency departments (PED) reported that almost half of them used N2O for analgesia when morphine was insufficient.(8) N2O administered for 20 minutes has also been shown to provide analgesia lasting up to 3 hours in inpatient children with VOC refractory to morphine infusions.(9) In addition to providing acute relief from pain and serving as a potentially opioid-sparing modality, N2O may also be able to provide long-term benefit due to its antagonism of NMDA receptors, as N2O has been shown to alleviate opioid-induced hyperalgesia and neuropathic pain in other populations. (10,13-15) The purpose of this pilot study is to describe the analgesic effect that N2O has on patients with SCD who have a VOC in the emergency department. The investigators have the following specific aims:

1. To determine whether N2O produces a clinically significant decrease in pain in patients with SCD who have a VOC that does not improve after initial standard treatment.
2. To determine the duration of analgesia produced by N2O in the aforementioned population.

Study Design:

We will conduct a single center pilot study in the pediatric emergency department (PED) of an urban, tertiary care children's hospital. The study is an interdivisional study between pediatric emergency medicine ([name]) and pediatric hematology ([name]).

Patient demographics for each patient will be documented, and a baseline neurological exam performed by the attending pediatric emergency medicine physician responsible for their care during that PED visit. An 8-week follow up physical examination will be performed if vitamin B12 levels obtained during the PED visit are low (see STUDY PROCEDURES: Follow-up Procedures). Vitamin B12 levels are being done solely for the conduct of this research. Our primary outcome will be the change in pain score from just prior administration to immediately following the discontinuation of N2O. The pain score will be measured using a numeric rating scale (NRS) of 0 (no pain) to 10 (worst pain), which is a valid and responsive scale for measuring pain in children older than 8 years of age. Our secondary outcomes will include:

- 1) the duration of analgesia resulting from N2O, which will be defined as the time elapsed from the discontinuation of N2O to the time at which the pain score becomes $>$ or $= 7/10$ (for those whose score decreased below 7), the patient receives additional analgesia, is discharged home, or is admitted to hospital. This time will be measured in minutes. Additional secondary outcomes will include,

2) complaints or physical findings suggestive of peripheral neuropathies (which may present as numbness, tingling, pain, or loss of feeling in fingers or toes; or weakness or difficulty moving the arms or legs) at the 8 week follow-up, as well as,

3) the presence of macrocytic anemia at 8 weeks time in patients who had low vitamin B12 levels at the time of enrolment.

STUDY PROCEDURES

- A) The following procedure is STANDARD care: Patients with SCD who present to the ED with VOC and a pain score of $\geq 7/10$ (i.e. severe pain) will receive IV fluids, NSAIDs, and IV morphine or hydromorphone. Blood work will be drawn and includes CBC, reticulocytes, and type and screen. After administration of the analgesics, the patient's pain will be reassessed after 15 minutes. If pain is still $\geq 7/10$, the patient will receive a "rescue" dose of IV morphine or hydromorphone. The patient's pain will be reassessed every 15 minutes and IV morphine or hydromorphone will be repeated until the pain score is $< 7/10$, at which point the patient's pain is reassessed (usually at least once every hour – there is no standardized interval) and the patient is transitioned to an oral analgesic at the attending physician's discretion, in conjunction with the hematology service.
- B) The following procedure is for RESEARCH purposes: Patients with SCD will be identified by a research assistant or study investigator if they have VOC and a pain score of $\geq 7/10$. If the patient has not already been consented (see informed consent), the primary physician providing care for the patient in the ED will be approached and asked to approach the patient and family to see if they would be interested in participating in the study. If they say yes, then a study investigator will approach the family to obtain informed consent. The reason why the family is approached at this point in time is so that the N2O treatment can be immediately initiated if the initial standard treatment is not effective, and so that there is no delay in care in providing analgesia when they have severe pain.

The patient will still receive the standard care of IV fluids, NSAIDs, and IV morphine or hydromorphone. In addition to the standard blood work, a vitamin B12 level will be drawn for study purposes. An additional 1 mL of blood (less than a quarter of a teaspoon) will be required. The pain score will be reassessed 15 minutes after the initial is still $\geq 7/10$, we will administer N2O at a concentration of 50% for 20 minutes. N2O is approved for use in the pediatric emergency department as per NYP Policy S100, and all standard procedures for administration and monitoring as per this policy will be followed.

Five minutes after discontinuation of the N2O, the patient's pain score will be assessed. If the pain score is still $\geq 7/10$, the patient will receive a "rescue" dose of IV morphine or hydromorphone, similar to the procedure in standard care, and will continue to be treated as per standard care.

If the patient's pain is $< 7/10$, the patient will have their pain reassessed by a study investigator every 15 minutes for the first hour, and then every 30 minutes after the first hour is completed OR whenever the patient volunteers or requests a pain assessment. Pain assessments will continue until the patient is discharged home. This frequency of pain assessment is the same, if not more frequent, than what occurs in standard care. The primary attending, in conjunction with the hematology service, will determine the transition to an oral analgesic and when to discharge the patient home.

- C) The following follow-up procedure is for RESEARCH purposes: Within 48 hours of the ED visit, a study investigator will review the laboratory results drawn at the time of enrollment. If the vitamin B12 level is

normal, then a study investigator or research coordinator will conduct a follow-up telephone call at week 8 to assess for any neurological symptoms. If the vitamin B12 level is low, the study investigators will notify the patient's attending hematologist within 24 hours and a follow up appointment will be scheduled at 8 weeks post enrollment at an outpatient clinic (hematology clinic or CTSA outpatient resource [if approved]). During this visit, one of the study investigators will conduct a physical examination and obtain laboratory tests (CBC and differential, vitamin B12) to evaluate for any potential long term side effects of receiving N2O (e.g. peripheral neuropathies, megaloblastic anemia).(7,17) Of note, the chances of these adverse events are low; they do not present acutely (onset is typically between 1 to 8 weeks); they are completely reversible with vitamin B12 supplementation; and have only been reported in the context of severe vitamin B12 deficiency and prolonged and repeated N2O administration.(7,17,18) Sickle cell patients are not expected to have vitamin B12 deficiency that would predispose them to these adverse events.(19) In discussion with our hematologists at NYP, it is their experience that our population of patients with SCD are at low risk of being deficient in vitamin B12.

Statistical Procedures:

Sample size: Twelve patients will be analyzed for this pilot study. This sample size was selected as there is minimal increase in precision expected around the mean and variance in the pain score change with additional patients enrolled. (16) To meet this analysis sample size, we anticipate that we may enroll up to 24 patients with severe VOC. This is because we expect that 50% of patients who are consented will ultimately not fulfill all inclusion criteria (i.e. their pain may be adequately managed with initial standard treatment, and may not require additional parenteral analgesia). The experience at our institution is that approximately 53% of patients with SCD who present to the PED with a VOC requiring parenteral analgesia as initial standard treatment require additional parenteral analgesics. We will not wait until patients have demonstrated a need for additional analgesia to begin the consent process, as this would delay the administration of analgesia in a patient with severe pain.

Statistical Plan: To assess the primary outcome, the mean difference and standard deviation in pain score before and immediately after N2O administration will be calculated for the NRS. Assessment of the secondary outcomes will be performed as follows:

- 1) the duration of analgesia will be determined by calculating the mean time and standard deviation (minutes) after discontinuation of N2O administration until the time at which the pain score becomes $>$ or $= 7/10$, the patient receives additional parenteral analgesia, is discharged home, or is admitted to hospital. The pain scores for each patient will also be plotted on a chart to illustrate the change in pain over time (y-axis = pain score, x-axis = time).
- 2) The presence of signs or symptoms suggestive of peripheral neuropathies will be documented, and the proportion calculated.
- 3) The presence of macrocytic anemia, if patients who have a low initial vitamin B12 level (see STUDY PROCEDURES: Follow-up Procedures) will also be documented and the proportion calculated.

Potential Risks:

There is limited data on the risks associated with N2O in patients with SCD. There are reports of long term side effects such as peripheral neuropathies and megaloblastic anemia).(7,17) The chances of these adverse events are low and have only been reported in case reports. They do not present acutely (onset is typically between 1 to 8 weeks), are completely reversible with vitamin B12 supplementation, and have only been

reported in the context of prolonged, continuous N2O administration (i.e. over 24 hours continuously), in the context of severe vitamin B12 deficiency, and prolonged and repeated N2O administration (e.g. 2 to 3 exposures a week for 6 weeks, and up to 3 hours each exposure). (7,17 18) Sickle cell patients are not expected to have vitamin B12 deficiency that would predispose them to these adverse events.(19) In discussion with our hematologists, it is also their experience that our population of patients with SCD is at low risk of being deficient in vitamin B12.

The risks associated with N2O in the general population are minimal (20,21). In a prospective survey of 35,828 administrations of 50% N2O, there was an incidence of 4.4% adverse events. The most frequent adverse events were nausea and/or vomiting (2%) and agitation or euphoria (1.8%). There was a 0.08% incidence of serious adverse events, including oxygen desaturation and cardiac arrest. However, both of these episodes were linked to inappropriate use of the administrative device and insufficient surveillance.(22) The rate of major adverse events when administering N2O concurrently with opioids is low. In one study of 7511 cases, there was no difference in the rate of major adverse events when 50% N2O was given with an opioid compared with when 50% N2O was given alone (0.33%).(23) In a separate report of 35,828 cases of 50% N2O administration, the overall rate of major adverse events when 50% nitrous administered alone was 0.08%, with the rate of major adverse events associated with any concomitant sedative administration (i.e. not exclusively opioids) being 0.03%.(22)

Potential Benefits:

The patient may experience pain relief of greater degree and duration than that achieved by receiving opioids. The patient may also receive more frequent assessment of their pain compared to the usual practice in the PED. The patient may benefit by avoiding short-term opioid-related side effects resulting from multiple doses of opioids acutely, such as hypotension, respiratory depression, or seizures. The patient may also benefit by attenuating, avoiding, or even improving long-term adverse events related to chronic opioid use, such as opioid-induced hyperalgesia, opioid tolerance, and chronic pain irrespective of VOC.

Alternatives:

The patient and parent may choose not to participate in the study.

Data and Safety Monitoring:

Pediatric emergency medicine attendings and fellows will implement the N2O intervention. These physicians will have all been trained and certified as per NYP policy to administer N2O in the PED. On an ongoing basis, each enrolled patient will be reviewed by the investigators to monitor adherence to study protocol, assess data quality, and to collect and review any acute adverse events and other subject safety matters. The study team as a whole will meet at the start of the study, and then every 6 months during patient enrollment. A Data and Safety Monitoring Board (DSMB) will be instituted, and will evaluate adherence to the protocol every 6 months, and will report any protocol violations to the IRB. In addition, a safety report will be provided to the DSMB after 3 (three) patients complete participation. The DSMB will consist of two pediatric subspecialists who are not involved with the study and have no vested interest in the study (TBD). Adverse Event Reporting: An adverse event is any untoward medical occurrence experienced by a subject. For each patient, the study investigators will evaluate adverse events from commencement until completion of the study. These adverse events will include, but are not limited to: nausea, vomiting, agitation, oxygen desaturation, apnea, respiratory distress, cardiac arrest, hypotension, megaloblastic anemia, and peripheral neuropathies. All unanticipated problems (including adverse events that meet the criteria of an unanticipated problem) will be reported to the IRB promptly, but not later than one week following the occurrence of the unanticipated problem or the PI's acquiring knowledge of the unanticipated problem, and at the time of continuing review.

REFERENCES

3. Benjamin LJ. Nature and treatment of the acute painful episode in sickle cell disease. In: Steinberg MH, ed. *Disorders of Hemoglobin: Genetics, Pathophysiology, and Clinical Management*: Cambridge; 2001: 671-710.
4. Ballas SK. *Sickle Cell Pain. Progress in Pain Research and Management*. Seattle, WA: IASP Press; 1998.

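### Aim 1 names patients who did not improve, but entry is by pain level, and a further fall from the initial opioid and NSAID cannot be separated from an N2O effect

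*Combined protocol and SAP*

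**What the plan says.** **Population.** Aim 1 (Study Purpose and Rationale) asks whether N2O gives a clinically significant decrease in pain in "patients with SCD who have a VOC that does not improve after initial standard treatment". Improvement is not defined there.

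**Entry to N2O.** Under Study Procedures B, patients are identified at a score of 7/10 or more. On initial treatment: "The patient will still receive the standard care of IV fluids, NSAIDs, and IV morphine or hydromorphone". On reassessment: "The pain score will be reassessed 15 minutes after the initial", after which the sentence is broken in the text available to me. If the score is still 7/10 or more, "we will administer N2O at a concentration of 50% for 20 minutes". The standard-care paragraph (Study Procedures A) supports the same time anchor: "After administration of the analgesics, the patient's pain will be reassessed after 15 minutes". Consent is sought early so that "N2O treatment can be immediately initiated if the initial standard treatment is not effective".

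**Outcome.** Study Design defines the primary outcome as the change in score from just before N2O to immediately after it stops. Study Procedures B takes the score five minutes after it stops. The Statistical Plan reports the mean and SD of that change, with no comparator and no use of the change before N2O.

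**Duration.** Aim 2 and Study Design treat the duration of analgesia as the product of N2O. Under the same heading the Statistical Plan adds a chart: "The pain scores for each patient will also be plotted on a chart to illustrate the change in pain over time". It gives no starting time for that chart.

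**The concern.** Two things do not fit together.

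First, the aim describes a lack of change and the procedure tests a level. The results would be reported for crises that did not improve, although some of the patients may have improved by up to 3 points before N2O.

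Second, N2O begins shortly after an IV opioid and an NSAID, and the outcome is a before-after difference in one group. If initial treatment goes on lowering pain during the outcome window, that fall enters the primary mean. It can also bring a patient below 7/10, and so into the duration outcome, or keep a patient there longer. Both aims would then credit N2O with something that the design cannot assign to it.

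**Working it through.** **The plan's own figure.** Twelve analysed patients, with 50% of those consented not going on to N2O: 12/(1 − 0.50) = 24, as stated. With the institutional figure of 53%, 12/0.53 = 22.6, or 23. Nothing below changes these numbers.

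**Timeline** (minutes after initial analgesics; Study Procedures A and B, Study Design).
- Reassessment and N2O start: about 15.
- N2O stop: 15 + 20 = 35.
- Outcome score: 35 if taken immediately, 35 + 5 = 40 if taken five minutes later.
- Primary window: about minute 15 to minute 35–40, so 20 to 25 minutes long.

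**Entry rule.** Whole-number scores of 7 to 10 at presentation and 7 to 10 at reassessment give 4 × 4 = 16 pairs. All qualify. In 6 the score has fallen (by 1, 2 or 3 points), in 4 it is unchanged and in 6 it has risen. This counts pairs, not patients; the documents do not say how often each occurs.

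**What a small further fall would do.** A patient who went from 10 to 7 fell at (10 − 7)/15 = 0.20 points per minute. To reach 6, and so enter the duration outcome with no N2O effect, that patient needs 1 more point in 20 to 25 minutes: 1/25 = 0.04 to 1/20 = 0.05 points per minute, a fifth to a quarter of the earlier rate. This is a break-even rate for the most extreme qualifying pair, not a prediction.

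**Share of the primary mean.** If initial treatment lowers pain by a further c points in the window and the observed mean fall is F, the share not due to N2O is c/F. With c = 0.5 to 2 and F = 3, all assumed: 0.5/3 = 17% to 2/3 = 67%.

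**Does it depend on prior improvement?** A simulation set the N2O effect to zero. Its assumptions were: presenting pain centred on 8.7 (SD 1.0); an eventual fall from initial treatment averaging 2, 3 or 4 points (SD 1.5); half-times of 10, 15 or 30 minutes; measurement error SD 0.7; outcome at minute 40. Over the nine settings the apparent mean fall from minute 15 to 40 was:
- all who qualified: 0.65 to 1.46 points;
- those with no improvement at minute 15: 0.81 to 1.66 points;
- those already improved, by subtraction: about 0.4 to 1.4 points. For example, with a 2-point fall and 30-minute half-time, (0.69 − 0.51 × 0.94)/0.49 = 0.43.

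In every setting the figure was larger in the non-improvers. Part of that is measurement error: an unimproved score is more often one that was read too high. Either way, lack of improvement at minute 15 does not mark a patient whose later fall can be credited to N2O.

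**The case against.** The strongest reply is that this is a 12-patient uncontrolled pilot whose stated purpose is descriptive. The inability to separate N2O from co-treatment is the missing control group under another name. The Statistical Plan has no test or interval, and Study Procedures B makes plain who receives N2O. Much of this stands, and it is why the remedy is limited to wording and description. It does not dispose of the point, because Aim 1 is phrased as determining whether N2O produces a decrease, Aim 2 credits the duration to N2O, and the population named in Aim 1 is not the one admitted.

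The reply is also right about three stronger readings that a reader might infer.
- *The opioid and NSAID were still lowering pain, so the bias always favours N2O.* The documents give no time course. They expect initial treatment alone to suffice in about half of consented patients, but do not say when relief comes. Waning relief or a worsening crisis would work against N2O.
- *The overlap arises because improvers are admitted, so splitting the primary mean and SD by prior improvement would expose it.* The simulation points the other way. The split would leave about six patients per group at best, and could make the non-improvers look clean when they are not.
- *All the data needed are already collected.* A presenting score is implied by how patients are identified, but opioid and NSAID times are not listed as study data.

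The 15-minute anchor in the research procedure is itself partly inferred from the standard-care paragraph, because the sentence is broken in the available text.

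**Conclusion.** The point holds in a limited form. The mismatch between Aim 1 and the entry rule is plain from the text. So is the overlap in time: the primary change covers about minute 15 to minute 35–40 after the opioid and NSAID, and the planned analysis has no means of telling a further fall due to those drugs from an N2O effect. This applies to improvers and non-improvers alike.

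The existence and size of such a fall cannot be established from the documents. The 17% to 67% range rests on an assumed further fall of 0.5 to 2 points and an assumed observed mean of 3; the simulated values rest on the inputs listed with them. They show that the issue could matter, not that it does. This is a worthwhile, nearly free correction to what the trial can claim, not a defect that invalidates it.

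**What to change.** 1. Reconcile Aim 1 with Study Procedures B by stating the population as patients whose pain is still 7/10 or more at the reassessment after initial treatment. This aligns the wording of the aim with the existing procedure and takes no view on the threshold.
2. In the Statistical Plan, list each patient's change from presentation to the pre-N2O score beside the primary change. Start the planned individual chart at presentation, with the N2O period marked, and analgesic times where they are recorded.
3. Word the Aim 1 and Aim 2 conclusions as change and duration following N2O added to recent opioid and NSAID, not as an effect of N2O alone.
4. Do not split the primary mean and SD by prior improvement.

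The cost is a few words, one extra column and a longer chart axis. Care and sample size are unchanged. The downside is a more modest headline claim. Items 2 and 3 do not remove the overlap; they let the reader see it and keep the conclusion within what the design supports.

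### Secondary outcome 3 counts macrocytic anemia present at week 8 without using the enrolment CBC, so anemia that predates N2O would count as a case (minor)

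*Combined protocol and SAP*

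**What the plan says.** The Study Design section gives secondary outcome 3 as "the presence of macrocytic anemia at 8 weeks time in patients who had low vitamin B12 levels at the time of enrolment". Item 3 of the Statistical Plan adds only that it "will also be documented and the proportion calculated". Neither place mentions new onset, change, or an earlier blood count.

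The blood count at enrolment exists. Under standard care in Study Procedures A, "Blood work will be drawn and includes CBC, reticulocytes, and type and screen". Study Procedures B adds a B12 level to that blood work and describes it ahead of the 15-minute pain reassessment that decides whether N2O is given.

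Study Procedures C says that within 48 hours of the visit "a study investigator will review the laboratory results drawn at the time of enrollment". Only the B12 result is given a consequence: "If the vitamin B12 level is low, the study investigators will notify the patient's attending hematologist within 24 hours". A visit follows at week 8, at which an investigator will examine the patient and "obtain laboratory tests (CBC and differential, vitamin B12) to evaluate for any potential long term side effects of receiving N2O". Patients with normal B12 get a telephone call about neurological symptoms and no blood test. On the anemia and neuropathy linked to N2O, the same section says that onset is usually one to eight weeks later and that "they are completely reversible with vitamin B12 supplementation".

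**The concern.** The outcome is meant to detect an effect of N2O, but its definition does not separate what was there before N2O from what came after. It applies only to patients whose B12 was low before the gas was given, which is the group in which a blood abnormality from the deficiency itself is most plausible. A patient who arrives with macrocytic anemia and still has it at week 8 is a case under the rule as written.

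The plan treats its other long-term outcome differently. For neuropathy, the Study Design section includes a baseline neurological examination. For anemia, the baseline measurement is taken but given no role.

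This is the only laboratory safety outcome among the stated outcomes, and the Potential Risks section acknowledges that little is known about N2O risk in sickle cell disease. A reported case should therefore at least be known to be new.

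**Working it through.** **1. The plan's own figure.** No number is attached to outcome 3. The enrolment figure in the Sample size paragraph can be checked: 12 analysed with 50% not qualifying gives 12 / (1 − 0.50) = 24, as stated. With the institutional rate of 53%, 12 / 0.53 = 22.6, rounded up to 23. The 12 used below is the planned analysis set.

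**2. The rule applied to each possible course in a low-B12 patient.**

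| Macrocytic anemia at enrolment | At week 8 | Outcome 3 as written | New-onset definition |
|---|---|---|---|
| No | Yes | Case | New case |
| Yes | Yes | Case | Listed as pre-existing |
| Yes | No | Not a case | Listed as pre-existing |
| No | No | Not a case | Not a case |

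The second row is the defect. It follows from the wording alone and needs no assumption about treatment.

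**3. How many patients this concerns.** The documents call the risk of deficiency low but give no prevalence, so I assume a range p. Expected number = 12p; chance of none = (1 − p)^12; chance of two or fewer is from the binomial distribution with n = 12.

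| p (assumed) | Expected of 12 | Chance of none | Chance of two or fewer |
|---|---|---|---|
| 2% | 0.24 | 78% | 99.8% |
| 5% | 0.6 | 54% | 98% |
| 10% | 1.2 | 28% | 89% |
| 20% | 2.4 | 7% | 56% |

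Zero to two evaluable patients is the likely result across this range.

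**4. What a proportion can say at that size.** One pre-existing case would be reported as 1/1 = 100% or 1/2 = 50%. The exact 95% interval for 1/2 is 1.3% to 98.7%. With no cases, the two-sided 95% upper limit is 1 − 0.025^(1/n): 97.5% for 0/1, 84.2% for 0/2 and 70.8% for 0/3. The individual values carry nearly all the information.

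**5. Supplementation, link by link.**
- Stated: the hematologist is told of a low B12, about eight weeks before the reading.
- Stated: the effect usually appears within one to eight weeks and reverses with supplementation.
- Not stated: that notification leads to supplementation, or when.
- Partly visible: B12 is repeated at week 8, so a corrected level would show, but not when it was corrected or whether anemia came and went.

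One link is missing, so masking of a true case is possible but not shown.

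**The case against.** The strongest reply is that little turns on this. Both specific aims concern analgesia, and outcome 3 is descriptive. Because an investigator reviews the enrolment results, a sensible author would probably look at the first CBC before calling an anemia new. The Data and Safety Monitoring section also lists megaloblastic anemia among adverse events evaluated for every patient throughout the study, so a case recognised clinically between visits would be reported. All of this stands and limits the severity. It does not change the definition, which still counts presence and assigns the enrolment CBC no use.

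A reader might go further in four ways that the documents do not support.

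- *That the baseline is missing.* It is drawn as standard care and reviewed; it is just not used in this outcome.
- *That supplementation will hide true cases.* The documents never say that supplementation follows notification, and the week-8 B12 level and adverse event reporting partly cover the possibility.
- *That a swing of 50 or 100 percentage points measures the defect.* It only reflects a denominator of one or two; one case would move a perfectly defined outcome just as far.
- *That absence of anemia at week 8 will be offered as evidence of safety.* No section plans such a claim.

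**Conclusion.** The point holds in a narrow form. As written, outcome 3 counts macrocytic anemia that predates N2O as a case, although the week-8 tests are there to look for N2O effects and the CBC that would separate the two is already taken. This rests on the wording and on one reading of sequence: that the enrolment blood is drawn with the initial work-up, before N2O, as Study Procedures B describes.

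Its practical size is small. Under an assumed prevalence of 2% to 20%, between 0.24 and 2.4 of the 12 patients are expected to enter the outcome, and it may well be empty. It would be tempting to conclude that a new-onset definition lets a case be attributed to N2O, or lets an effect be excluded. It does neither: with one arm and probably zero to two evaluable patients, attribution stays weak after the change. The gain is that pre-existing anemia is no longer reported as an outcome of treatment. Severity: minor.

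**What to change.** - Define outcome 3 as new macrocytic anemia at week 8 in patients with low B12 at enrolment, judged by comparing week-8 MCV and hemoglobin with the same patient's enrolment CBC. Make the same change in the Statistical Plan.
- Report macrocytosis already present at enrolment separately, not as a new case.
- Record whether B12 was supplemented between enrolment and week 8, and when, so that a negative reading can be interpreted.
- Beside the proportion, list each low-B12 patient with enrolment and week-8 B12 and CBC values and supplementation status.

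The cost is a few extra data fields, some chart review and revised wording. Fewer patients will count as clean cases. No new blood draw or visit is needed, and neither the notification of the hematologist nor any part of care changes.

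### Does planning for up to 24 consents leave this pilot short of its 12 analysed patients?

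*Combined protocol and SAP*

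**What the plan says.** Statistical Procedures, Sample size, makes one firm statement: "Twelve patients will be analyzed for this pilot study". The reason given is a precision rule of thumb, that "there is minimal increase in precision expected around the mean and variance in the pain score change with additional patients enrolled". The number to consent follows from it: "To meet this analysis sample size, we anticipate that we may enroll up to 24 patients with severe VOC". The allowance is explained by the statement that "we expect that 50% of patients who are consented will ultimately not fulfill all inclusion criteria", because some patients will respond to initial standard treatment. The same paragraph cites local experience: "approximately 53% of patients with SCD who present to the PED with a VOC requiring parenteral analgesia" as first treatment go on to need more of it.

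Consent is sought before anyone knows whether the patient will qualify, so that treatment is not delayed. The number who qualify is therefore random. Study Procedures, part B, also allows for consent given before the visit ("If the patient has not already been consented (see informed consent"). The informed-consent section it points to is not in the supplied text.

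The primary analysis in the Statistical Plan is a mean change in pain score with its standard deviation. No test, power or confidence interval is planned.

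**The concern.** Dividing the target by the expected qualifying rate gives the number of consents that yields the target on average. With a random yield, close to half of such studies would fall below target if consenting stopped at that number. The plan says that 12 will be analysed, yet the supplied text has no rule for continuing past 24, for replacing patients who do not qualify, or for reporting a smaller number. The precision argument covers only going above 12 and is silent on falling below it.

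A reader could therefore be unsure whether a final count of 9 to 11, or a 25th consent, follows the plan. Under Data and Safety Monitoring, the board reviews adherence every 6 months and reports violations to the IRB, so the status of a 25th consent might have to be decided.

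**Working it through.** **Inputs, all from the Sample size paragraph:** target 12; consents up to 24; qualifying rate p = 1 − 0.50 = 0.50; local rate 0.53. The local figure is the rate of needing further parenteral analgesia, which is close to, but not the same as, the trial's trigger of a score of 7 or more at the 15-minute reassessment.

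**1. The plan's own figure.** 12 / 0.50 = 24, which reproduces exactly. At the local rate, 12 / 0.53 = 22.6, or 23, so 24 leaves a small margin: 24 × 0.53 = 12.7 expected.

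**2. Chance of a shortfall if 24 is a cap.** Let X be Binomial(24, p), with one independent chance per consent and no loss after qualifying. Then P(X < 12) = Σ C(24, x) pˣ (1 − p)²⁴⁻ˣ over x = 0 to 11.

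| | p = 0.50 | p = 0.53 |
|---|---|---|
| P(X < 12) | 0.419 | 0.308 |
| P(X ≥ 12) | 0.581 | 0.692 |
| P(X ≤ 9) | 0.154 | 0.094 |
| P(X ≥ 10) | 0.846 | 0.906 |
| Mean analysed, stopping at 12 | 11.0 | 11.4 |
| Mean analysed, given a shortfall | 9.7 | 9.9 |

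Check at p = 0.50, by symmetry: P(X = 12) = 0.161, and (1 − 0.161) / 2 = 0.419.

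**3. Sensitivity.** At assumed rates of 0.45 and 0.60, P(X < 12) is 0.615 and 0.114. The documents give no rate of loss after qualifying. With an assumed 5% or 10% loss, the effective rate is 0.475 or 0.45 (from 0.50) and 0.5035 or 0.477 (from 0.53). P(X ≥ 12) is then 0.48 or 0.38, and 0.59 or 0.49.

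**4. If 24 is a forecast.** Consenting runs until 12 qualify, and there is no shortfall. The same 42% (or 31%) becomes the chance that more than 24 consents are needed. When that happens, the mean excess is 4.6 (or 4.0) consents.

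**5. What a shortfall costs.** The plan reports no interval, so this is only a gauge. The 95% half-width for a mean, in units of the SD of the change, is t(0.975, n − 1) / √n.

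| n | Half-width (SD) | Relative to n = 12 |
|---|---|---|
| 12 | 0.635 | – |
| 11 | 0.672 | 0.672 / 0.635 = 1.06 |
| 10 | 0.715 | 0.715 / 0.635 = 1.13 |
| 9 | 0.769 | 0.769 / 0.635 = 1.21 |

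**6. What a formal rule would cost.** For 80% assurance of 12, the limit would be 28 consents (p = 0.50) or 26 (p = 0.53). For 90% it would be 31 or 29. Compared with a cap of 24, the 90% limits raise mean consents from 22.1 to 23.7, or from 21.4 to 22.4.

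**The case for a change.** The strongest case for a change is that the gap is real and a sentence would close it. The commitment to 12 is firm, the supporting number is soft, and the forecast reading does not expressly permit a 25th consent. Each consent also has a price: an extra 1 mL of blood for vitamin B12, and week-8 follow-up. In Study Procedures, part C, that follow-up starts when "a study investigator will review the laboratory results drawn at the time of enrollment" and is not limited to patients who received N2O. The calculation in step 2 is also favourable in one respect, since it allows for no loss after qualifying.

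The silence of the supplied text stands, and so does the arithmetic. Three things limit its force.

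- The wording around 24 is hedged and is expressly there to serve the 12. Nothing says that consenting stops at 24 if 12 has not been reached.
- The binomial model gives each consent one chance. Because consent may precede the visit, a patient who does not qualify in one crisis might do so in a later one. The supplied text does not settle this. If it is allowed, the shortfall probabilities are too high.
- The possible rewrites gain little. A limit chosen for 80% or 90% assurance serves a target the plan never set, and it permits more consents to reach it. Keeping 24 as a cap and analysing everyone treated would remove the stop at 12. The count would then exceed 12 with probability 42% (p = 0.50) to 54% (p = 0.53), against the stated 12.

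**Conclusion.** The concern does not call for a change. The figure of 24 is correct as the expected number of consents for 12 analysable patients. The 31% to 42% chance of a shortfall holds only if 24 is a cap, each consent gives one independent chance, and nobody is lost after qualifying. The plan states none of these, and the first is the less natural reading of its text.

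Even on that reading the consequence is small. At least 10 patients would be analysed with probability 85% to 91%, and precision at 10 or 11 would be 13% or 6% worse than at 12. That is for a descriptive mean and SD with no decision rule attached. Whether 24 is a cap, and what is reported below 12, is missing detail that the team can settle by treating 12 as the target and reporting the number reached. Writing it down would not alter what the trial concludes.

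The judgement would be weaker if the true qualifying rate were well below 50% or losses after qualifying were substantial. The documents give no sign of the first and no figure for the second.
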